10.6 Subgroup analyses

10.6.1 Effectiveness

The GIHS and GAIS endpoints will be analyzed in the needle group and the cannula group separately, using the same analysis method as for the primary analysis for GIHS, and descriptively for GAIS (control subjects will be pooled). CCI

CCI

CCI

CMH tests will be used for comparison of responder rates, as well as confidence intervals of the differences in responder rates. These will be displayed in graphs.

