4.1 General outline

This is a prospective, randomized, evaluator-blinded, no-treatment controlled, parallel group, multi-center US study to evaluate the effectiveness and safety of *Restylane-L* for correction of Infraorbital Hollows. Approximately 329 subjects will be included (CCI) to treatment (using needle or cannula) or to no treatment group. In the treatment group approximately 146 subjects will get injections using needle and approximately 136 subjects using cannula. Approximately 47 subjects will be randomized to no-treatment at baseline. The sites will be selected to use either needle or cannula for injection of all subjects randomized to treatment at their particular site. Approximately half of the sites will be using needle and the other using cannula for injection.

All randomized subjects' will have a GIHS score of 2 (Moderate) or 3 (Severe) with no more than one grade difference between the left and right side at baseline.

 <small>EST. 1981</small>	<small>Title</small> 43USTT1904 CSP Infraorbital Hollows	<small>Doc id</small> MA-40833
--	--	--

Effective date: 2021-12-15 20:29

Investigator blinding will be accomplished by using a Treating Investigator to administer the treatments and a Blinded Evaluator, to whom randomization and treatment are concealed, to conduct the blinded assessments. In addition, the Blinded Evaluator should not be allowed to retrieve study supplies or be present during the opening of the study supplies or injection procedure. All documents with information regarding study products and randomization assignment should be kept in a separate binder not available to the Blinded Evaluator. Safety assessments will be performed by non-blinded personnel.

Eligible subjects randomized to receive treatment will be injected by the Treating Investigator at Day 1. Optional touch-up treatment may be administered after 1 month of initial treatment, if deemed necessary by Treating Investigator and subject to obtain optimal aesthetic improvement. Optimal aesthetic improvement is defined as at least 1 grade improvement, from baseline, on the GIHS and best correction that can be achieved as agreed by the Treating Investigator and the subject. If optional touch-up is performed, a 72 hours telephone call, 14 day and 1 month follow-up visits should be scheduled.

Effectiveness and safety data will be collected for 12 months following the first injection.

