4.4 Randomization and blinding

4.4.1 Randomization

Approximately 329 subjects will be randomized in a **CC** ratio to treatment with *Restylane-L* or no treatment. Before starting the study, a computer generated randomization list will be prepared under the supervision of a designated statistician from the Sponsor. The randomization list will be stratified by FST group (I-III, IV, and V-VI). The FST I-III group will be further stratified by study site. The FST IV and FST V-VI groups will be further stratified at needle or cannula level (needle sites pooled into a needle stratum, and cannula sites pooled into a cannula stratum). Randomization numbers will be allocated in ascending sequential order to each subject. Randomization will be performed using an Interactive Response System by assigning each subject to *Restylane-L* or no treatment according to the randomization list.

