10.4 Effectiveness analysis

10.4.1 Primary effectiveness analysis:

Responder rate based on the GIHS as assessed live by the Blinded Evaluator at month 3 after baseline will be the primary effectiveness endpoint. A responder will be defined as a subject with at least 1 point improvement from baseline on both sides of the face concurrently. For a significant result, the two-sided p-value of the comparison of responder rates between the treated and untreated subjects at month 3, using the Cochran-Mantel-Haenszel (CMH) test stratified by injection tool, needs to be smaller than 0.05.

The null hypothesis will be that there is no relationship between responder rate and treatment group (i.e. the responder rate is the same in both groups). The alternative hypothesis will be that there is a relationship between responder rate and treatment group (i.e. the responder rate is different in the two groups).

	Title 43USTT1904 CSP Infraorbital Hollows	Doc id MA-40833
--	---	---------------------------

The estimates of the responder rate in each treatment group will be presented as well as the difference in responder rates. Corresponding confidence intervals for responder rates and the difference in responder rates along with the p-value for the difference will also be presented.

CCI

10.4.2 Secondary effectiveness analysis:

Responder rates (defined as at least 1 point improvement from baseline on both sides of the face concurrently) based on the GIHS as assessed by the Blinded Evaluator at month 6, 9, and 12 after baseline and at 3 and 6 months after optional treatment will be analyzed in the same way as the primary effectiveness endpoint. No correction for multiplicity will be done; p-values obtained for any endpoint other than the primary will only be provided for ease of interpretation of the results.

All other secondary effectiveness analyses will be done descriptively as appropriate.

10.5 **Safety analysis**

Number and percentage of subjects reporting each pre-defined, expected, post-treatment symptoms, as collected in the 28 days diary, will be presented in total and by maximum severity. Number of days with the event will be presented by treatment group and category: 1, 2-7, 8-13, and 14-28.

All AEs will be coded according to MedDRA and summarized by system organ class (SOC), preferred term (PT) and treatment.

A summary of all AEs will be provided, which will include:

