#### Multiple Comparisons/Multiplicity

Multiplicity will be adjusted for in the primary effectiveness subgroup analysis and is further detailed in Section 2.4.3.2.

	Title 43USTT1904 Statistical analysis plan - Tear Trough	Doc id
GALDERMA 657, 1981		MA-42205

2022-08-17 17:26

For all secondary effectiveness endpoints, no correction for multiplicity will be done; p-values obtained for any endpoint other than the primary will only be provided for ease of interpretation of the results.

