#### 2.4.3 Primary effectiveness analysis

The primary effectiveness analysis will be done using the mITT Population. To evaluate the effectiveness of Restylane-L versus no-treatment control in the correction of Infraorbital Hollows, the GIHS responder rates (defined in Section 1.3.1) at Month 3 after baseline will be compared using the CMH test stratified by injection tool at the 5% significance level (2-sided).

The null hypothesis will be that there is no relationship between GIHS responder rate and treatment group (i.e. the responder rate is the same in both Restylane-L and no treatment groups). The alternative hypothesis will be that there is a relationship between responder rate and treatment group (i.e. the responder rate is different in the two groups). For a significant result, the two-sided p-value of the comparison of GIHS responder rates between the treated and untreated subjects at Month 3 using the CMH test needs to be smaller than 0.05.

The estimates of the GIHS responder rates in each treatment group will be presented as well as the difference in responder rates (Restylane-L responder rate – No Treatment responder rate). Corresponding 95% CI for the treatment group GIHS responder rates and the difference in responder rates along with the p-value for the difference will also be presented. The normal approximation (Wald) method will be used to calculate the 95% CI for the individual treatment group GIHS responder rates as well as the 95% CI for the difference in responder rates.

Effective date: 2021-12-1713:25

Version: 3.0

Title 43USTT1904 Statistical analysis plan - Tear Trough

Doc id

[figure not shown]
Print date:

MA-42205

2022-08-17 17:26

Effective

Effective

Print date:

[figure not shown]
2022-08-17 17:26

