#### 2.4.4 Secondary analysis

All secondary endpoint analyses will be conducted using the ITT Population. In general, "by treatment group" refers to the Restylane-L Needle, Restylane-L Cannula, Restylane-L (pooled), and the No Treatment group.

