#### 2.7 Determination of Sample Size

Due to the public health emergency related to the COVID-19 pandemic during 2020, steps have been taken to ensure patient and practitioner safety in alignment with FDA Guidance dated May 11, 2020 (Guidance on Conduct of Clinical Trials of Medical Products during COVID-19 Public Health Emergency). Most notably, in partnership with clinical sites and the IRB, optional remote assessment procedures for efficacy and safety endpoints has been implemented to ensure safety and respect localized and elective restrictions. Therefore, the sample size has been increased during the conduct of the study to ensure a sufficient number of subjects in the mITT population used in the assessment of the primary effectiveness endpoint.

The study was initially planned to enroll a total sample size of approximately 238 subjects; approximately 204 randomized to treatment with Restylane-L ( $\sim$ 102 injected using needle, and  $\sim$ 102 injected using cannula) and approximately 34 randomized to no treatment.

Based on information on missing data and the number of remote visits performed at study sites so far, the study is now planned to enroll approximately 329 subjects; approximately 282 will be randomized to treatment with Restylane-L (~146 will be injected using needle, and ~136 will be injected using cannula) and approximately 47 will be randomized to no treatment in order to achieve the required number of mITT subjects in each stratum.

2022-08-17 17:26

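### Do the single-tool GIHS analyses in Protocol 10.6.1 need an own-tool control set, given that control subjects will be pooled?

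*Protocol*

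**What the plan says.** Protocol section 10.6.1 says that GIHS and GAIS endpoints will be analysed in the needle and cannula groups separately, "using the same analysis method as for the primary analysis for GIHS, and descriptively for GAIS (control subjects will be pooled", where the bracket closes. Redacted text follows.

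The primary method it refers to is in Protocol section 10.4.1: a two-sided p-value, "using the Cochran-Mantel-Haenszel (CMH) test stratified by injection tool, needs to be smaller than 0.05". SAP section 2.4.3 adds the interval: "The normal approximation (Wald) method will be used to calculate the 95% CI" for each group's rate and for the difference.

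Tool is not randomised. Protocol section 4.1: "The sites will be selected to use either needle or cannula for injection of all subjects randomized to treatment at their particular site". Under Protocol section 4.4.1, randomisation is by site for Fitzpatrick types I-III, and types IV and V-VI are stratified by tool, with "needle sites pooled into a needle stratum, and cannula sites pooled into a cannula stratum".

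The SAP's Multiple Comparisons paragraph states: "Multiplicity will be adjusted for in the primary effectiveness subgroup analysis", and refers to section 2.4.3.2, which cannot be read in the public copy. SAP section 2.7 explains the larger enrolment as "in order to achieve the required number of mITT subjects in each stratum". For secondary endpoints, SAP section 2.4.4 says that results by treatment group "refers to the Restylane-L Needle, Restylane-L Cannula, Restylane-L (pooled), and the No Treatment group", so there is one control column. Section 2.4.4.1 nevertheless keeps the CMH test stratified by injection tool.

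**The concern.** Every control subject was randomised against one tool only, the one used at that subject's site or in that tool stratum. If all controls serve both single-tool comparisons, about half of the control group in each is an external comparison within the trial. Any difference between needle sites and cannula sites in how untreated subjects are rated would pass into the estimated effect, in opposite directions for the two tools.

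There is a second worry. If the test stays stratified by tool while the Wald interval is computed crudely on all controls, the p-value and the interval in one table would rest on different control groups.

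The stake is the reading of the single-tool results. The SAP adjusts a subgroup analysis of the primary endpoint for multiplicity, and enrolment was raised to reach a number per stratum. If both statements refer to tool, which is plausible but not stated in the visible text, these are more than casual subgroups, and readers might take each as a fully randomised effect of one technique.

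**Working it through.** **Inputs.** Protocol sections 4.1 and 10.11 and SAP 2.7 give 146 needle, 136 cannula and 47 untreated subjects. The allocation ratio is redacted. Responder rates below are assumptions, because the documents show none.

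**Plan's own figures.** 146 + 136 = 282 and 282 + 47 = 329, as stated. 282/47 = 6.0 and, for the initial plan, 204/34 = 6.0, so the ratio is 6:1.

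**Controls per tool**, assuming the same ratio in both strata:
- needle sites: 47 × 146/282 = 24.3
- cannula sites: 47 × 136/282 = 22.7

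Share of controls from the other tool's sites: 22.7/47 = 48% (needle comparison) and 24.3/47 = 52% (cannula comparison).

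**Shift in the estimate if controls are pooled** = share × gap in untreated response between site groups:

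| Assumed gap (points) | Needle shift | Cannula shift |
|---|---|---|
| 2 | 1.0 | 1.0 |
| 5 | 2.4 | 2.6 |
| 10 | 4.8 | 5.2 |

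**What a tool-stratified CMH does with the extra controls.** In each stratum the test adds (treated responders − expected) to the numerator and n1·n0·m1·m0/(n²(n−1)) to the variance, where n1 and n0 are treated and control counts and m1 and m0 are responders and non-responders. A stratum of controls only has n1 = 0, so both terms are zero.

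Illustration for needle: 96/146 treated responders, 4/24 needle-site controls, 5/23 cannula-site controls (a gap of about 5 points).
- Own-tool controls: 10.118²/5.022 = 20.38.
- Stratified, with the cannula-site controls as a second stratum: again 20.38.
- Unstratified, 96/146 v 9/47: 16.570²/8.866 = 30.97.

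**Wald interval**, difference ± 1.96·√(p1(1−p1)/n1 + p0(1−p0)/n0):
- Own-tool: 65.8% − 16.7% = 49.1 points (32.3 to 65.9).
- Pooled: 65.8% − 19.1% = 46.6 points (33.0 to 60.2).

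The estimate moves by 2.5 points and the conclusion is the same.

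**Error rate if stratification were dropped.** Exact binomial enumeration with no true effect: 20% response at cannula sites, needle sites at the rate shown, 24 needle-site and 23 cannula-site controls. The multiplicity method is not visible, so two alpha levels per tool are shown.

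| Needle-site rate | Cannula, α 0.025 | Needle, α 0.025 | Cannula, α 0.05 | Needle, α 0.05 |
|---|---|---|---|---|
| 20% | 2.4% | 2.4% | 5.0% | 4.9% |
| 18% | 2.3% | 2.8% | 5.0% | 5.5% |
| 15% | 2.7% | 4.5% | 6.0% | 7.5% |
| 10% | 5.0% | 12.1% | 10.7% | 16.2% |

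The excess for needle is all against needle. The two-sided total understates the cannula side: rejections falsely favouring cannula at α 0.025 are 0.9/1.3/2.1/4.9% down the rows, against 1.25% nominal in that direction.

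**What an own-tool analysis would cost and show.** At 60% v 30% and α 0.025, power is 71% (146 v 24) and 69% (136 v 23), against 92% for each tool with 47 controls. It could hardly detect the gap at issue: with 24 and 23 controls at 20%, the 95% margin on the difference between the two control groups is 1.96·√(0.16/24 + 0.16/23) = 23 points.

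**The case for a change.** The strongest case for acting is that the structural fact is documented and the remedy is cheap. Pooling for GIHS is a natural reading of the sentence, and the single No Treatment group in the SAP fits it. The single-tool results may carry a multiplicity adjustment, and one sentence on the control set plus one supportive table per tool would leave the primary analysis, alpha and sample size as they are. Under the unstratified reading, a 10-point gap would roughly double the cannula error rate.

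The 48% and 52% stand, as does the point that a label would be accurate. The rest is weaker.

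- The inflated error rates need GIHS pooling and also the loss of stratification. The visible words point the other way, since the method carried over is the stratified test.
- The mismatch between p-value and interval needs stratification kept with a crude interval, so it cannot occur together with the inflation.
- Untreated subjects receive no injection before Month 12, so the tool cannot act on their Month 3 rating. A gap would have to come from differences between sites or evaluators, averaged over about nine sites per tool under common eligibility, scale and responder definition.
- With a 23-point margin, an own-tool table could not separate a 2-, 5- or 10-point gap from chance.

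**Conclusion.** No change to the plan follows. The visible text leaves a detail of the single-tool GIHS analysis unclear, but redacted text follows the sentence in Protocol 10.6.1 and SAP 2.4.3.2 is unreadable, so neither the control-set rule nor an own-tool sensitivity analysis can be called absent. If the detail is open, it is one that analysts settle when programming the table: one control set and one stratification for test, difference and interval.

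Pooling is an openly pre-specified trade-off. At the assumed 60% v 30% it offers about 92% rather than 70% power per tool, in exchange for a shift of about half of any gap between the site groups. A 2-point gap moves the estimate by 1 point and leaves the error rate near nominal. Gaps of 5 to 10 points would matter more, and only if stratification were dropped would they reach the test.

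This rests on planned rather than observed counts, a 6:1 ratio in both strata, and assumed responder rates. Evidence that untreated response differs materially between needle and cannula sites would reopen the question; the documents contain none. The primary comparison pools both tools and stratifies by tool, so it is not affected.

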10.6.2 Safety

In order to evaluate the safety of treatment using needle and cannula respectively, AE data will be summarized by needle, cannula and no treatment separately.

CCI

10.7 Handling of drop-outs and missing data

Number of missing values will be summarized and reported as appropriate.

For mITT analysis of the Blinded Evaluator GIHS responder rate at month 3 after baseline (primary endpoint), CCI. Impact of missing data on the primary endpoint will be evaluated by performing sensitivity analysis based on the baseline observation carried forward (BOCF) method, and the observed cases.

	Title 43USTT1904 CSP Infraorbital Hollows	Doc id MA-40833
--	---	---------------------------

All other effectiveness endpoints will be evaluated based on the observed cases in ITT.

Descriptive statistics of all safety data will be performed on observed cases in the Safety population.

10.8 Interim analysis

Not applicable.

10.9 Data monitoring committee

Not applicable.

10.10 Withdrawals and deviations

All withdrawn subjects will be listed individually, including at least subject number, date and reason for withdrawal, and last visit performed.

Subjects with CSP deviations will be listed individually, including subject number and observed deviation. Depending on the seriousness of the deviation, subject might be excluded from the PP population, which shall be documented prior to database lock.

Deviations from the statistical plan will be documented in the Clinical Study Report.

[figure not shown]
10.11 Sample size

Due to the public health emergency related to the COVID-19 pandemic during 2020, steps have been taken to ensure patient and practitioner safety in alignment with FDA Guidance dated May 11, 2020 (Guidance on Conduct of Clinical Trials of Medical Products during COVID-19 Public Health Emergency). Most notably, in partnership with clinical sites and the IRB, optional remote assessment procedures for efficacy and safety endpoints has been implemented to ensure safety and respect localized and elective restrictions. Therefore, the sample size has been increased during the conduct of the study to ensure a sufficient number of subjects in the mITT population used in the assessment of the primary effectiveness endpoint.

The study was initially planned to enroll a total sample size of approximately 238 subjects; approximately 204 randomized to treatment with *Restylane-L* (~102 injected using needle, and ~102 injected using cannula) and approximately 34 randomized to no treatment.

Based on information on missing data and the number of remote visits performed at study sites so far, the study is now planned to enroll approximately 329 subjects; approximately 282 will be randomized to treatment with *Restylane-L* (~146 will be injected using needle, and ~136 will be injected using cannula) and approximately 47 will be randomized to no treatment in order to achieve the required number of mITT subjects in each stratum.

CCI

	Title 43USTT1904 CSP Infraorbital Hollows	Doc id MA-40833
--	---	---------------------------

Effective date: 2021-12-15 20:29

CCI

11. Protection of personal data

All processing of personal data must be carried out in accordance with national legislation concerning the protection of personal data. The Institution and the Investigator are responsible for complying with all requirements pursuant to national legislation in which the Institution and the Investigator are located. The Sponsor will ensure that all requirements for data processing are fulfilled.

The Investigator understands that clinical studies conducted under an IDE are exempt from the study subject identifier confidentiality provisions of the Health Insurance Portability and Accountability Act of 1996 (HIPAA), and the study subject should be made aware of this exception in the informed consent. The Institution and Investigator are jointly responsible for providing sufficient information to all subjects to enable them to give their informed consent not only to the participation in the investigation, but also to the processing of Personal Data. Such information includes information regarding the purposes of the processing, the length of time during which Personal Data will be stored, the right of access to stored Personal Data and the right to correction or purging of incorrect or obsolete Personal Data. A subject may also withdraw his or her consent at any time.

A subject who withdraws his or her consent to the processing of Personal Data must be considered to have withdrawn from the investigation, but the data collected until the consent was withdrawn may be used in the statistical analyses.

Authorized representatives from the Sponsor or a RA may visit the investigational site to perform audits/inspections, including source data verification, i.e., comparing data in the subjects' medical records and the eCRF. Data and information will be handled with strict confidentiality.

The study shall include collection and processing of personal data as specified in the Regulation (EU) 2016/679 (General Data Protection Regulation, GDPR) on the protection of individuals with regard to the processing of personal data. For the purposes of the study, Sponsor will be considered the data controller, and Institution and PI will both be considered data processors.

12. Quality Control and Quality Assurance

